# Visit EoT of extended treatment period (end of study visit)

The following actions/measures will be performed for patients of Arm A and Arm B:

- questioning for adverse events and concomitant medication
- measurement of blood pressure and heart rate (after resting for at least 3 min in supine position)
- measurement of forearm blood flow
- laserdopplerfluxometry (LDF)
- measurement of arterial stiffness
- efficacy laboratory parameter for endothelial function and coagulation:
- efficacy laboratory for composite of biomarkers of inflammation
- safety laboratory parameter
- assessment of metabolic marker
- return of study drug / drug accountability
- advice patient for further treatment after end of study

<del>Visit</del> <del>Week</del>	<del>V0</del> <del>day-28</del>	<del>V1</del> day 0 ±4d	<del>∀2</del> <del>2 ±2d</del>	<del>V3 (⊤v)</del> 4 ±2d	₩4 <del>8 ±2d</del>	<del>V5 (⊺∨)</del> <del>12 ±2d</del>	<del>∨6</del> <del>20 ±2d</del>	<del>Dispensed</del> <del>medication</del>
<del>Rivaroxa-</del> <del>ban</del>	-	<del>90</del> <del>(3 Packs)</del>	<del>210</del> <del>(7 Packs)</del>	-	<del>330</del> <del>(11 Packs)</del>	-	-	<del>630</del>
aspirin	-	<del>50</del> <del>(1 Pack)</del>	<del>50</del> <del>(1 Pack)</del>	-	<del>50</del> <del>(1 Pack)</del>	-	-	<del>150</del>

#### Original wording Dispensing of IMP (section 5.7):

Visit Week	V0 day -28	V1 day 0 ±4d	V2 2 ±2d	V3( т v) 4 ±2d	V4 8 ±2d	V5(тv) 12 ±2d	V6 20 ±2d	Dispensed medication
Rivaroxa- ban	-	90 Tabl. (3 Packs)	210 Tabl. (7 Packs)	-	330 Tabl. (11 Packs)	-	270 Tabl. (9 Packs)	630 (+270) Tabl. = 21 (+9) Packs
Aspirin	-	50 Tabl. (1 Pack)	50 Tabl. (1 Pack)	-	50 Tabl. (1 Pack)	-	100 Tabl. (2 Packs)	150 (+100) Tabl. = 3 (+2) Packs

#### Revised wording Dispensing of IMP (section 5.7):

 TABLE 12: DRUG DISPENSE FOR FIRST TREATMENT PERIOD (1 PACK RIVAROXABAN CONTAINING 30 TABLETS; 1 PACK ASPIRIN CONTAINING 50 TABLETS);

OPTIONAL: DISPENSE OF IMP AT V6 FOR PATIENTS PARTICIPATIONS TO EXTENDED TREATMENT PERIOD

Visit Week	V7 (TV) 24 ±2d	V8 28 ±2d	V9 (TV) 32 ±2d	V10 36 ±2d	V11 (TV) 40 ±2d	V12 (TV) 44 ±2d	V13 52 ±2d	Dispensed medication
Rivaroxa- ban	-	210 Tabl. (7 Packs)	-	510 Tabl. (17 Packs)	-	-	-	720 Tabl. = 24 Packs
Aspirin	-	50 Tabl. (1 Pack)	-	150 Tabl. (3 Packs)	-	-	-	200 Tabl. = 4 Packs

TABLE 13: DRUG DISPENSE FOR EXTENDED TREATMENT PERIOD (80 OF 188 PATIENTS) (1 PACK RIVAROXABAN CONTAINING 30 TABLETS; 1 PACK ASPIRIN CONTAINING 50 TABLETS)

## **Statistical Analysis Plan (SAP)**

**Primary trial objective:** Evaluation of efficacy defined as the difference of change

of forearm blood flow with venous occlusion

plethysmography at baseline and after forearm ischemia after 20 weeks treatment between rivaroxoban and aspirin

therapy.

Additionally the difference of arterial stiffness after 52 weeks treatment (extension study) between rivaroxoban

and aspirin therapy will be evaluated.

**Trial design:** Multicenter, prospective, active controlled,

randomized, 2 parallel arms, open

interventional clinical trial

Investigational

medicinal product:

Rivaroxaban

#### **Abbreviations**

**Abbreviation Definition** 

ADR Adverse Drug Reaction

AE Adverse Event

ANCOVA Analysis of Covariance b.i.d. (Bis in Die) twice a day BMI Body Mass Index CI Confidence Interval

CRNM Clinical Relevant Non-Major CSV Clinically significant value

CTCAE Common Terminology Criteria for Adverse Events

ECG Electrocardiogram

eCRF Electronical Case Report Form

FAS Forearm Blood Flow

GmbH Gesellschaft mit beschränkter Haftung ICH International Council for Harmonization

LDF Laser Doppler Fluxometry
LLOQ Lower Limit of Quantification

Max Maximum
Min Minimum
OR Odds Ratio

PCSV Potentially clinically significant value

PPS Per Protocol Set
PT Preferred Term
PWA Pulse Wave Analysis
PWV Pulse Wave Velocity
q.d. (quaque die) daily

SADR Serious Adverse Drug Reaction

SAE Serious Adverse Event
SAP Statistical Analysis Plan
SAF Safety Analysis Set
SOC System Organ Class

SOP Standard Operating Procedure

STD Standard Deviation

vs. versus

#### 1 Rational of the statistical analysis plan

The purpose of the statistical analysis plan (SAP) is to ensure the credibility of the study results by prespecifying statistical approaches for the analysis of study. The SAP is intended to be a comprehensive and detailed description of strategy and statistical techniques to be used to realize the analysis of data for the MicroVasc-DIVA study.

This plan may be revised during the study to accommodate protocol amendments and to adapt to unexpected issues in study execution or data that affect planned analyses. These revisions will be based on blinded review of the study and data.

#### 2 Investigational Plan

#### 2.1 Study design

This will be a multicenter, open-label, controlled study with two treatment arms running in parallel. A total of 188 patients of both genders and older than 18 years with type 2 diabetes and documented high cardiovascular risk and low grade inflammation will be randomly assigned to one of two treatment groups:

Arm A: treatment group: Rivaroxaban (5 mg b.i.d for the duration of 20 weeks, 52 weeks

duration for patients participating in the extension)

Arm B: control group: Aspirin (100 mg q.d. for the duration of 20 weeks, 52 weeks

duration for patients participating in the extension)

[figure not shown]

Figure 1: Trial overview

#### 2.2 Visit schedule

7 visits will be performed during the study. Visits will take place at week –2 (screening – V0), day 0 (randomization/baseline – V1), at week 2 (V2), 4 (V3), 8 (V4), 12 (safety/compliance – V5) and week 20 (end of treatment for the first study period with vascular function test – V6).

Additionally, 80 patients of the study population will perform 7 additional visits during the extension period. These visits will start after week 20. Patients attending the extension period performed a total of 14 study visits. The additional visits will take place at week 24 (V7), week 28 (V8), week 32 (V9), week 36 (V10), week 40 (V11), week 44 (V12) and week 52 (end of treatment extension - V13).

VISIT	VO	V1	V2	V3 (TV)	V4	V5 (TV)	V6
WEEK	day -28	day 0 (+/- 4 d)	2 (+/- 2 d)	4 (+/- 2 d)	8 (+/- 2 d)	12 (+/- 2 d)	20 (+/- 2 d)
	SCREEN	BASELINE	TREAT	TREAT	TREAT	TREAT	EOT
STUDY INFORMED CONSENT	✓						√ A
SCREENING OF INCLUSION AND EXCLUSION CRITERIA	*						
VITAL SIGNS (RADIAL PULSE, BLOOD PRESSURE)	~	~	√		4		✓
RANDOMIZATION*	✓						
BODY HEIGHT	✓						
WAIST/HIP CIRCUMFERENCE BODY WEIGHT	1						4
ECG	✓						
MEDICAL HISTORY	✓						
CONCOMITANT MEDICATION/ ACUTE DISEASES	✓	~	1	1	4	~	4
ARTERIAL STIFFNESS		✓					✓
FOREARM BLOOD FLOW		~					✓
INFLAMMATION LABORATORY 		✓					✓
SAFETY LABORATORY 	✓	✓	✓		4		✓
EFFICACY LABORATORY 		✓					✓
METABOLIC MARKER 		✓					✓
SCREENING LABORATORY 	>						
CARDIOVASCULAR MARKER		✓					1
LDF INVESTIGATIONS		~					*
PLATELET ACTIVATION/ MITOGENIC POTENTIAL		1					4
ADVERSE EVENT REPORTING		✓	*	✓	4	✓	✓
DISPENSING/RETURN OF MEDICATION/ DRUG ACCOUNTABILITY		~	~		*		~
PREGNANCY TEST	~						

Table 1: Study visits and parameters

VISIT	V7 (TV)	V8	V9 (TV)	V10	V11 (TV)	V12 (TV)	V13
WEEK	24	28 (+/- 2 d)	32 (+/- 2 d)	36 (+/- 2 d)	40	44 (+/- 2 d)	52 (+/- 2 d)
	(+/- 2 d) TREAT	TREAT	TREAT	TREAT	(+/- 2 d) TREAT	TREAT	EOT EXTEN- SION
STUDY INFORMED CONSENT FOR EXTENSION PERIOD	*						
VITAL SIGNS (RADIAL PULSE, BLOOD PRESSURE)		~		*			*
BODY HEIGHT							~
WAIST/HIP CIRCUMFERENCE BODY WEIGHT							*
CONCOMITANT MEDICATION/ ACUTE DISEASES	>	*	>	>	>	>	*
ARTERIAL STIFFNESS							✓
FOREARM BLOOD FLOW							*
INFLAMMATION LABORATORY 							√
SAFETY LABORATORY 		4		√			*
EFFICACY LABORATORY 							*
METABOLIC MARKER 							*
LDF INVESTIGATIONS							√
ADVERSE EVENT REPORTING	✓	✓	✓	✓	✓	4	✓
DISPENSING/RETURN OF MEDICATION/ DRUG ACCOUNTABILITY		*		*			*

Table 2: Study visits and parameters of extended treatment period

#### 2.3 Study objectives

Objectives of this clinical trial are the in vivo assessment of microvascular function using different non-invasive techniques and the in vitro assessment of biomarkers of endothelial damage, inflammation and coagulation/fibrinolysis before and after treatment with either aspirin or rivaroxaban in type 2 diabetic patients with high cardiovascular risk and inflammation. Furthermore possible functional interactions between mononuclear blood cells and platelets as well as expression of mRNA (and protein) within these cells before and after treatment in vitro will be assessed.

#### 2.3.1 Primary objectives

Primary objective is the difference of change of forearm blood flow with venous occlusion plethysmography at baseline and after forearm ischemia after 20 weeks treatment between rivaroxoban and aspirin therapy.

Additionally the difference of arterial stiffness after 52 weeks treatment (extension study) between rivaroxoban and aspirin therapy will be evaluated.

### 2.3.2 Secondary objectives

- Change of peripheral skin microcirculatory function (measured by Laser Doppler fluxometry;
   LDF) after 20 and 52 weeks of treatment
- LDF baseline
- LDF after ischemia (endothelial function)
- arterial stiffness measured by Mobilograph (IEM Inc.) after 20 weeks of treatment
- laboratory markers for endothelial function
- VCAM, ICAM, E-Selectin, ADMA, Nitrotyrosin, P-Selectin, CD40-L
- Microalbuminuria, eGFR
- composite of biomarkers of inflammation
- hsCRP, PAI-1, MCP-1, MMP-9, fibrinogen, leucocytes, MPO, IL-6, IL-8
- side effects: major bleeding according to ISTH, symptomatic thromboembolic events
- metabolic marker: HbA1c, lipids: triglycerides, LDL-C, HDL-C
- coagulation: von Willebrand-Factor, Fibrinogen, Prothrombinfragment 1 + 2, D-Dimer, Protein C, Protein S, TAT, Quick, aPTT
- cardiovascular marker: NT-proBNP, hs-Tnl, GDF-15, MR-ANP

Additional secondary objective for extension period:

• Difference of change of forearm blood flow with venous occlusion plethysmography at baseline and after forearm ischemia after 52 weeks treatment.

#### 2.3.3 Explorative study objective(s)

Assessment of platelet activation, measurement of mitogenic potential and risk benefit assessment.

#### 2.4 Sample size calculation

The first primary variable is the change of forearm blood flow with venous occlusion plethysmography ( $\Delta$ FBF) after forearm ischemia after 20 weeks of treatment. The sample size calculation is based on the following assumptions:

- Hypotheses: H0:  $\mu_{\Delta FBF, Riva} \leq \mu_{\Delta FBF, ASS}$ H1:  $\mu_{\Delta FBF, Riva} > \mu_{\Delta FBF, ASS}$
- Application of t-test for independent samples
- Type I error:  $\alpha = 0.05$
- Power: 1-ß = 0.90
- Estimated dropout rate: 25 %
- Minimum of expected clinical relevant difference between the groups in changes of maximal forearm blood flow ( $\Delta$ FBF) = 1.2 ml/100ml with an estimated standard deviation (STD)  $\sigma$  = 2.4 ml/100ml

Sample size should be at least N = 188 Patients (i.e. N/2 = 94 patients per arm) in order to achieve a valid number of 141 patients (per protocol analysis).

Additionally, the second primary variable is the difference of PWV between treatment groups at EOT Extension (after 52 week of treatment). The sample size calculation is based on the following assumptions:

H0: μPWV, Riva = μPWV, ASS

• H1:  $\mu_{PWV, Riva} \neq \mu_{PWV, ASS}$ 

• Type I error:  $\alpha = 0.05$ , t-test for independent samples

• Power: 1-ß = 0.80

Estimated dropout rate: 20 %

• Minimum of expected clinical relevant difference between the groups in PWV = 0.7 m/s with an estimated standard deviation (STD) of  $\sigma$  = 1.0 m/s

Sample size should be N=80 patients (40 patients per arm) to achieve a valid number of 66 patients for per protocol analysis.

In summary the necessary sample size would be N=188 patients for the study up to week 20 including 80 patients for the extension up to week 52.

#### 3 Analysis Sets

For the analysis, patients not fulfilling the selection criteria of the trial ("all randomized") will be excluded from the statistical analysis. Only casuistic reports will be provided for this group.

#### 3.2 Safety Analysis Set (SAF)

All patients having received at least one application of study medication are generally evaluable for safety and will be included in the safety analysis set.

#### 3.3 Per-Protocol Set (PPS)

Analyses of efficacy endpoints will be performed on the per protocol analysis set (PPS) defined as the subset of subjects of the FAS who have provided complete data of the target variable of interest at the first (V1) and last visit (V6/V13) and who have no major protocol deviations thought to impact the efficacy conclusions of the trial. The classification of protocol violation as major and minor will be done in a data review meeting that will take place after the database is clean.

#### 4 Analysis Variables

#### 4.1 Demographics

The following demographic characteristics will be summarized at baseline day 0: age (year), gender, race.

#### 4.2 Medical history

Information on following diagnostics will be recorded at baseline day 0: Pregnancy Test (done yes/no), result of pregnancy test (pregnant yes/no), ECG (yes/no), if "yes", ECG result ("normal", "minor findings", "major findings") Duration of diabetes
In- and exclusion criteria

#### 4.3 Concomitant medication and acute diseases

Medications taken will be recorded from the day of informed consent until the EOT visit (day 0-week 52). Patients who received a concomitant medication at any point of time will be counted in the category "yes". All patients who did not receive any concomitant medication in the course of the study will be counted in the category "no".

#### 4.4 Drug administration

The drug amount dispensed and returned will be recorded. Compliance (proportion of drug taken compared to drug dispensed) will be monitored.

#### 4.5 Efficacy Variables

Efficacy variables will be measured at day 0, weeks 20 and week 52:

Forearm blood flow (FBF) (mL/100mL): IR baseline, IR post-ischemic, IR post-ischemic (AUC)

#### Extension:

Arterial stiffness measured by pulse wave analysis: Pulse wave velocity (m/s), index of augmentation (%), peripheric and central blood pressure systolic/diastolic (mmHg)

Skin blood flow (measured by Laser Doppler):

Depth pre-ischemic blood flow (U), depth post-ischemic blood flow (U), shallow pre-ischemic blood flow (U) and shallow post-ischemic blood flow (U)

#### 4.6 Laboratory Variables

Several categories of laboratory variables are assessed:

- screening laboratory (day -28):
   hemoglobin, hematocrit, ALAT, ASAT, creatinine (PAP method), blood cell count (leucocytes,
   erythrocytes, platelets), total bilirubin, sodium, potassium, eGFR, HDL-C, triglycerides,
   cholesterine, urinary albumin/creatinin ratio, creatinine urine, hsCRP (if not available before
   screening visit according to in- and exclusion criteria), PAI1 (optional), urine pregnancy test
- inflammation laboratory (day 0, weeks 20, 52): hsCRP, PAI-1, MCP-1, MPO, IL-6, IL-8, MMP-9, fibrinogen
- efficacy laboratory for endothelial function and coagulation (day 0, weeks 20, 52):
   VCAM-1, ICAM-1, E-Selectin, P-Selectin, CD40L, von Willebrand factor, ADMA, nitrotyrosin, urinary albumin/creatinin ratio, eGFR, UACR, creatinin (serum), fibrinogen (immunolog), prothrombin fragment 1 and 2, TAT, D-Dimer, protein C, protein S, Quick, aPTT
- metabolic markers (day 0 (if not available, using of values at screening visit), weeks 20, 52):
   HbA1c, triglycerides, LDL-C, HDL-C, total cholesterine
- cardiovascular markers: NT-proBNP, hs-Tnl, GDF-15, MR-ANP
- bioassay data (subpopulation at day 0 and week 20): Thrombocytic micro-particles, vasodilatorstimulated phoshoprotein (VASP), serine-positive thrombocytes und thrombocyte proliferation rate.

#### 4.7 Safety Variables

#### 4.7.1 Vital Signs

Vital Signs will be collected in terms of:

Height (cm) (day 0, week 52)

Weight (kg), BMI (kg/m2), Waist and Hip circumference (cm) (day 0, weeks 2, 8, 20, 28, 36, 52) Radial pulse (bpm), systolic/diastolic blood pressure (mmHg) (day 0, weeks 2, 8, 20, 28, 36, 52)

#### 4.7.2 Safety laboratory

Safety laboratory variables will be monitored (day 0, weeks 2, 8, 20, 28, 36, 52): hemoglobin, hematocrit, ALAT, ASAT, creatinine (PAP method), blood cell count (leucocytes, erythrocytes, platelets), total bilirubin, sodium, potassium, eGFR

#### 4.7.3 Adverse Events and Serious Adverse Events

Adverse events and serious adverse events will be collected from first intake of study medication and then at each visit until the end of the study (day 0-week 52).

Bleedings (yes/no). If "yes" bleeding is classified as:

- major bleeding ("major")
- clinically relevant non-major bleeding ("CRNM")

Patients with major bleeding at any time in the course of the study will be counted in the category "major". All patients with CRNM but never "major" at any time will be counted in the category "CRNM". Only patients with minor bleedings but never CRNM are counted in the category "minor".

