#### SYNOPSIS

Sponsor	GWT-TUD GmbH [name] 01307 Dresden Germany		
Coordinating Principal Investigator	[name]		
Title of the clinical trial	Microvascular and antiinflammatory effects of Rivaroxaban compared to low dose aspirin in type 2 diabetic patients with very high cardiovascular risk and subclinical inflammation		
Indication	Rivaroxaban 5 mg b.i.d vs. aspirin 100 mg qd in patients with type 2 diabetes and very high cardiovascular risk		
Phase	III b		
Type of trial, trial design, methodology			
Number of subjects	188 patients in (94 patients each arm)		
Treatment Groups	Arm A (treatment group): Arm B (control group):	Rivaroxaban 5 mg ASS 100 mg qd	b.i.d
Treatment period	20 weeks + additional 32 weeks (extension study for 80 patients)		
Time plan	First patient first visit (FPFV): Last patient first visit (LPFV): Last patient last visit (LPLV): Database Lock: Final study report:	April 2015 July 2017 August 2018 December 2018 April 2019	

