#### Adverse events:

All AE/SAE will be assessed and documented by the investigator according to the categories detailed below.

- Seriousness (yes/no):
  - Patients with SAE at any time in the course of the study will be counted in the category SAE. All patients with AE but not serious at any time will be counted in the category AE.
- Intensity (mild, moderate, severe)
- Causal relationship (yes/no)
- Action taken with study treatment (drug withdrawn, drug interrupted, dose reduced, dose not changed, dose increased, not applicable, unknown)
- Other specific treatments (none, remedial drug therapy, other)
- Outcome (recovered/resolved, recovered/resolved with sequelae, not recovered/not resolved, life-threatening, fatal, unknown)

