#### 6.9 Treatment exposure and observation period

The duration of treatment exposure period during the study is calculated as:

(last drug administration date – first drug administration date) + number of days to next visit after last drug administration.

The duration of observation period during the study is calculated as:

last contact date - randomization date +1.

The duration of exposure and the duration of observation period will be summarized for each treatment group (FAS, PPS and SAF).

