#### 6.12.4 Bleedings

The results for major, CRNM, minor and total bleeding will be documented. Total bleeding includes any bleeding event (including CRNM, minor and major bleeding). These analyses will be performed on SAF and PPS.

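### The AE and bleeding percentages pool 20-week and 52-week follow-up, so they estimate neither risk, and the comparison between arms is sound only if extension uptake and dropout are balanced

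*SAP*

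**What the plan says.** - **Follow-up.** The protocol synopsis gives the treatment period as "20 weeks + additional 32 weeks (extension study for 80 patients"). SAP 2.1 likewise sets 20 weeks, with a 52-week "duration for patients participating in the extension". SAP 2.4 plans "N=188 patients for the study up to week 20 including 80 patients for the extension up to week 52".
- **Entry to the extension.** The visit schedule in Protocol 4.12.2 requires an additional consent at the week-20 visit. The trial is open-label (Protocol 5.10). Forty extension patients per arm is a sample-size target, and no rule enforces it.
- **Collection window.** Under SAP 4.7.3, AEs and SAEs "will be collected from first intake of study medication and then at each visit until the end of the study", which the SAP glosses as day 0 to week 52. Only extension patients can complete that window.
- **Counting.** Bleeding is classified by the worst category reached at any time in the study: "Patients with major bleeding at any time in the course of the study will be counted in the category" of major bleeding. For serious events, "Patients with SAE at any time in the course of the study will be counted in the category SAE".
- **Denominator and test.** Safety is analysed in everyone with at least one application of study drug (SAP 3.2, 6.12), and bleeding also in the PPS. Of bleeding, SAP 6.12.4 says only this: "The results for major, CRNM, minor and total bleeding will be documented". The mock-ups in 7.8.3 and 7.8.4 show patients (N, %) by arm with a p-value for the proportions, and event counts below. SAP 6.3 names Fisher's exact and chi-square tests.
- **Exposure.** SAP 6.9: "The duration of exposure and the duration of observation period will be summarized for each treatment group". The mock-up in 7.5 compares both durations between arms.

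**The concern.** Efficacy is reported separately at week 20 and week 52, but AEs and bleeding are not. Neither document sets a week-20 cut-off, a split by extension status, a rate per person-time or a time-to-event analysis for safety.

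A patient due 52 weeks has 2.6 times the time at risk of one due 20 weeks (52/20). A percentage pooled over both groups does not refer to any stated period. A reader cannot set it beside a 20-week or a 52-week figure from elsewhere.

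The comparison between arms has a second, conditional weakness. Entry to the extension is voluntary, comes after randomisation, and is made by patients and investigators who know the treatment. If more patients continue in one arm, or more drop out of the other, the arm with more time at risk shows a higher percentage even when the hazards are equal.

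Protocol 2.5 calls bleeding the major risk of oral anticoagulation and says that no direct comparison of the bleeding risk of these two regimens had been published. These tables would supply that comparison.

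**Working it through.** **Inputs from the plan.** 188 patients, 94 per arm; 80 in the extension, 40 per arm; 20 or 52 weeks (SAP 2.1, 2.4). The plan states no expected AE or bleeding percentage, so there is none to reproduce. The 94 per arm does reproduce: a one-sided 5% t-test with 90% power, difference 1.2 and SD 2.4 needs 70 per arm, and 70/0.75 = 93.3, rounded up to 94.

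**Assumptions.** The 20-week risk r is varied from 5% to 40%. The hazard is constant and equal in both arms, so there is no true difference. There is no dropout.

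**Planned time at risk.** 188 × 20 + 80 × 32 = 3,760 + 2,560 = 6,320 patient-weeks. Extension patients supply 80 × 52 = 4,160, or 66%.

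**Formulas.** h = −ln(1 − r)/20. The 52-week risk is R = 1 − exp(−52h). With m extension patients in an arm, the pooled proportion is [m × R + (94 − m) × r]/94.

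**Example, r = 5%.** h = 0.05129/20 = 0.002565 and R = 1 − exp(−0.1334) = 12.5%.
- m = 40: (40 × 0.1249 + 54 × 0.05)/94 = 8.2%
- m = 48: (48 × 0.1249 + 46 × 0.05)/94 = 8.8%
- m = 32: (32 × 0.1249 + 62 × 0.05)/94 = 7.5%

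**Range** (differences taken before rounding):

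| Assumed 20-week risk | 52-week risk | Pooled, 40/40 | Pooled, 48/32 | Difference, 48/32 |
|---|---|---|---|---|
| 5% | 12.5% | 8.2% in each arm | 8.8% vs 7.5% | 1.3 points |
| 10% | 24.0% | 15.9% in each arm | 17.1% vs 14.8% | 2.4 points |
| 20% | 44.0% | 30.2% in each arm | 32.3% vs 28.2% | 4.1 points |
| 40% | 73.5% | 54.3% in each arm | 57.1% vs 51.4% | 5.7 points |

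**Stress case.** A 55/25 split at r = 5% gives 9.4% versus 7.0%, a ratio of 1.34.

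**Effect on the test.** With no true difference, and r from 10% to 40%, the simulated rejection rate of a two-sided 5% Fisher test is about 2.4% to 2.9% at 40/40. At 48/32 it is about 5% to 8%.

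**How likely is imbalance by chance alone?** If 80 of 188 entered regardless of arm, the hypergeometric probability of 44/36 or worse is about 0.30. For 48/32 or worse it is about 0.027, and for 55/25 or worse about 0.00002.

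**If the hazard halves after week 20** (assumed; r = 5%): R = 1 − 0.95 × exp(−32 × 0.002565/2) = 8.8%. Then 48/32 gives 7.0% versus 6.3%, and 55/25 gives 7.2% versus 6.0%.

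**After the fix.** On a common window to week 20, equal hazards give equal percentages (5% and 5% when r = 5%) whatever the extension split.

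**The case against.** The plan supplies more than a bare percentage. It shows numbers of events as well as patients, and it compares exposure and observation durations between arms, so an imbalance in follow-up would be visible. The AE listings carry start date and study day of onset (SAP 6.12.3), so events up to week 20 can be identified. All of this stands. What is missing is any pre-specified use of it: the durations do not enter the percentages or the p-values, and the event-count rows have no person-time either.

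The distortion between arms is also conditional. At 40/40 with equal dropout it is zero. At 48/32 and r = 5% it is 1.3 points, about one patient in 94. A split of 55/25 would require continuation to depend strongly on arm; the open-label design allows that, but nothing in the documents predicts it. A constant hazard may overstate the shift if those who tolerate treatment are the ones who continue. These limits stand.

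A reader might infer that the planned comparison is biased as it stands, or that the plan gives no information on follow-up. The documents support neither reading. The first fails at the plan's own 40/40 target, and the second overlooks SAP 6.9 and the mock-up in 7.5.

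Finally, the protocol calls the trial explorative, and bleeding is neither a primary endpoint nor powered. That argues for a modest remedy, but it does not justify leaving the period undefined.

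**Conclusion.** The point holds in two parts of different strength.

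- **Certain from the text.** Each pooled AE and bleeding percentage mixes 20-week and 52-week follow-up, at any extension split. Its size depends on the assumed risk and hazard: 8.2% where the 20-week risk is 5% and the 52-week risk 12.5%, or 15.9% where they are 10% and 24.0%.
- **Conditional.** The comparison between arms is unbiased at 40/40 with equal dropout, and shifts if uptake or dropout differs by arm. A 48/32 split moves it by 1.3 to 5.7 points over the assumed 20-week risks of 5% to 40%, and by less if the hazard falls after week 20. The 55/25 figures are a stress case and not a forecast.

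The event risks, hazard shapes and uneven splits are assumptions, because the documents give no expected rates. The patient-weeks ignore the planned dropout of 25% and 20%.

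**What to change.** In SAP 4.7.3, 6.12.3 and 6.12.4, and in the mock-ups 7.8.3 and 7.8.4:

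1. Make the main AE and bleeding comparison the patients with an event from first dose to week 20, in all treated patients. Attach the p-value to this table.
2. Show weeks 20 to 52 in a separate table, limited to patients who entered the extension, with their number per arm as denominator.
3. Add event rates per 100 patient-years by arm, using the observation time already derived in SAP 6.9.
4. Optionally, add a time-to-first-bleed analysis.

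The cost is a few extra tables from AE dates already recorded. No visit, treatment or data item changes. Label: cheap improvement.
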